7.4 VARIABLES

7.4.1 EXPOSURES

The exposure measures are based on the prescription of the two long-acting bronchodilators under study, namely LABAs and tiotropium, as well as ICS. As described in the data analysis section, the as-treated analysis, which is the main analysis, will consider exposure as current use of LABA-TIO or LABA-ICS within the treated groups defined as within the 60-day period after the prescriptions' dispensing dates.

[figure not shown]
7.4.2 OUTCOME(S)

7.4.2.1 PRIMARY OUTCOME(S)

The primary outcome event is the first COPD exacerbation to occur after cohort entry. The event is defined as a hospitalization for COPD (severe exacerbation) or the prescription of an oral corticosteroid, namely prednisolone (moderate exacerbation).

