propensity score-matched approach. The potential comparator subjects will be selected from the base cohort by forming time-based exposure sets defined by the calendar year of entry into the base cohort for the LABA-TIO and LABA-ICS simultaneous prescription users. To allow matching on the propensity of treatment choice, we will compute high-dimensional time-conditional propensity scores (TCPS) by identifying all available data (e.g., diagnoses, procedures, medications) in the one-year period prior to the date of cohort entry for each time-based exposure set using Cox proportional hazards regression. Then, for each LABA-TIO exposed subject, and starting chronologically with the first one, we will identify a matched comparator subject from the members of the subject's time-based exposure set. We will first match subjects on sex, previous components of the study treatment (LABA only, TIO only, ICS alone, none of these) and the presence of an acute COPD exacerbation in the year before cohort entry. The matched reference subject will then be selected as the one with the closest time-conditional propensity score in the matched set, after trimming within each exposure set, and allowing a maximum difference in scores of 0.05 for a match. In the absence of a tight propensity score match, we will take the closest and the analysis will be complemented by an adjustment for the propensity score.

After matching, the subjects in the study cohort will be followed up for up to one year from cohort entry (the date of the matched set), with follow-up ending at the earliest of the date of a switch or addition of either an ICS for the LABA-TIO group or of tiotropium to the LABA-ICS group, death, one year after cohort entry, December 31, 2016, or the end of coverage in the practice, whichever occurs first.

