7.4.2.2 SECONDARY OUTCOME(S)

The first secondary outcome is the rate of COPD exacerbations over the one-year follow-up. This outcome will be based on the number of hospitalizations and on the number of courses of treatment with an oral corticosteroid. A gap of at least 30 days between treatment courses will be required to consider the exacerbations as separate events. The second secondary outcome is the occurrence of the first hospitalization for community-acquired pneumonia (serious pneumonia). Pneumonia will be defined from the following ICD10 codes: J10.0; J11.0; J12-J18; J22; J69; J85.0; J85.1; J86. This definition has been used successfully in COPD [P07-09514; P16-10095].

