7.4.3 COVARIATES

Sex, previous treatment and previous acute COPD exacerbation, as well as calendar year of cohort entry, are all matching factors and will thus inherently be accounted for.

Although we will use the high-dimensional approach to identify variables entering the time-conditional propensity score, some key covariates will be highlighted. First, we will identify key lifestyle variables available in the CPRD, known to be risk factors and potential confounders, including the body mass index (BMI), smoking status and excessive alcohol consumption. Missing data for smoking status and BMI will be entered as an additional category in the model. We will also explore the possibility of obtaining blood eosinophils measured in the year prior to cohort entry and will use this information only if complete.

Second, the occurrence of the study outcomes prior to cohort entry will be identified during the one-year baseline period and adjusted for in the analysis if found to be imbalanced between treatment groups after propensity score matching. In particular, COPD exacerbations occurring in the 30 days prior to the study cohort entry date, a marker of COPD exacerbation risk, will be identified separately from those occurring previously during the baseline year. In addition, the severe exacerbations requiring hospitalizations will be counted, while the moderate exacerbations will be identified from counts of prescriptions for oral corticosteroids.

Third, use of other respiratory drugs during the baseline period will be included as a measure of COPD severity. Thus, the number of prescriptions for short-acting beta-agonists, anticholinergics, methylxanthines and muscarinic antagonists used during the year prior to cohort entry will be identified. As well, the number of prescriptions for antibiotics for a respiratory condition will be counted. In addition, we will count the number of prescriptions for the study drugs used during the baseline period. These will be combined into a single variable because of the study design which inherently selects patients into the two study groups according to their prior LABA, TIO or ICS use. Finally, for each of the cohorts, baseline co-morbidity will be measured using diagnoses and prescriptions for various conditions observed often in patients with COPD, namely cardiovascular disease, diabetes, thyroid disease, renal failure, autoimmune disease and cancer, all in the year prior to cohort entry.

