The analysis of the secondary objective related to the rate of exacerbation will be based on the negative binomial regression models, which corresponds to a Poisson regression model adjusted for between-subject variation in exacerbations, with the same approach to covariate adjustment as the primary analysis. A 30-day gap between events will be used to distinguish between one continuous exacerbation and two separate events. The analysis of the secondary objective related to the risk of pneumonia will use a time-dependent Cox proportional hazard regression model with an as-treated approach, similar to that of the primary analysis.

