7.11 LIMITATIONS OF THE RESEARCH METHODS

Several potential biases inherent to any observational study need to be considered. Because this is primarily a study of effectiveness, confounding by indication is among the most important potential sources of bias in the absence of randomisation. However, matching the two groups on prior COPD exacerbations, prior treatments and on the propensity score should limit this potential bias. The possibility of information bias due to misclassification of the outcomes or exposure is present. Indeed, the CPRD includes prescriptions written by the GP rather than filled or taken by patients, which could be a source of misclassification of exposure and the outcome of a moderate exacerbation defined by prescriptions. With respect to the other outcome definitions, the linkage to HES data to identify hospitalization for COPD exacerbation and for community-acquired pneumonia should also reduce the potential for misclassification of outcomes.

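### The 30-day separation rule is not stated for the primary outcome, so a repeat prednisolone prescription for an episode treated just before cohort entry counts as the first event

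*Combined protocol and SAP*

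**What the plan says.** **Primary outcome.** Section 7.4.2.1: "The primary outcome event is the first COPD exacerbation to occur after cohort entry", and "The event is defined as a hospitalization for COPD (severe exacerbation) or the prescription of an oral corticosteroid, namely prednisolone (moderate exacerbation". It sets no gap from an earlier course and no washout. Section 7.3 starts follow-up on the day of cohort entry.

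**Separation rule.** Section 7.4.2.2, for the rate of exacerbations: "A gap of at least 30 days between treatment courses will be required to consider the exacerbations as separate events". Section 7.9.1, in the paragraph on the secondary analyses: "A 30-day gap between events will be used to distinguish between one continuous exacerbation and two separate events". Neither mentions the primary outcome or cohort entry.

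**Handling of recent exacerbations.** Section 7.3 matches on "the presence of an acute COPD exacerbation in the year before cohort entry" and builds the propensity score by "identifying all available data (e.g., diagnoses, procedures, medications) in the one-year period prior to the date of cohort entry". Section 7.4.3 identifies exacerbations in the 30 days before entry separately. Prior outcomes are "adjusted for in the analysis if found to be imbalanced between treatment groups after propensity score matching". Section 7.9.1 adds propensity-score deciles to the Cox model. Section 7.6 adds adjustment for general severity, without saying whether the 30-day indicator is included.

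**Limitations.** Section 7.11 admits "misclassification of exposure and the outcome of a moderate exacerbation defined by prescriptions", on the ground that prescriptions may not be filled or taken. It does not mention repeated courses.

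**The concern.** Treatment may be stepped up around the time of an exacerbation, so some patients will probably enter the cohort soon after a prednisolone course. A second prescription shortly after entry may belong to that same episode. Counting it as the first event has three consequences.

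- It is not a new exacerbation by the standard the plan applies to its rate outcome, so the two outcomes define an exacerbation differently.
- It ends the patient's time at risk for the primary outcome, so a later genuine exacerbation is never counted there.
- It falls in the first 30 days. The as-treated analysis uses a 60-day window for current use and censors patients who stop, so early events carry more weight than they would with a full year of follow-up.

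Matching and covariate adjustment address differences in risk between arms. They do not reclassify an event.

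**Working it through.** **1. The definitions side by side.** Take prednisolone on days -10 and +8. The interval is 18 days, which is under 30, so the rate-outcome rule makes it one exacerbation that began before entry. Under section 7.4.2.1, day +8 is a prednisolone prescription after entry and is therefore the first event. This step needs no assumption about frequency.

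**2. The plan's own figures (section 7.7: 3,000 per arm, 50% one-year risk).** Treating 0.90 as a ratio of one-year risks, 50% v 45%: standard error = sqrt(0.50×0.50/3000 + 0.45×0.55/3000) = 0.01288; 0.05/0.01288 - 1.96 = 1.92; power 97.3% (stated 97%). The same method gives over 99.9% for 0.85 (stated 99%) and 92.5% for severe events, 15% v 12% (stated 92%).

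**3. Balanced carry-over, by hand.** Let a share c of each arm have a carry-over prescription. Observed risk = c + (1 - c) × true risk.

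| c | True ratio 0.90 | True ratio 0.85 |
|---|---|---|
| 1% | 0.4555/0.505 = 0.902 | 0.43075/0.505 = 0.853 |
| 10% | 0.505/0.55 = 0.918 | 0.4825/0.55 = 0.877 |

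On this scale, power for 0.90 falls from 97.3% to 93.7% at c = 10%. A true ratio of 1.00 stays at 1.00 for any c.

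**4. Balanced carry-over in a Cox model.** Assumptions, none of them from the documents:
- 10-33% of patients had an exacerbation in the 30 days before entry, and 10-30% of those have a repeat, so c runs from 0.10×0.10 = 1% to 0.33×0.30 = 10%.
- The reference hazard averages ln 2 per year (from the 50% risk), and recent exacerbators have 1.5 times the risk.
- The pre-entry course is uniform over the 30 days before entry, and the repeat is uniform from entry to day 30 after that course.
- Full one-year follow-up, with the 30-day indicator in the model.

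The large-sample Cox estimate was obtained by numerical integration. Power = Φ(sqrt(D)/2 × |ln HR| - 1.96), where D is the number of events in 6,000 patients.

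| True HR | Carry-over | D | HR read | Power |
|---|---|---|---|---|
| 0.90 | none | 2,880 | 0.900 | 81% |
| 0.90 | 1% | 2,903 | 0.902 | 80% |
| 0.90 | 10% | 3,123 | 0.917 | 68% |
| 0.85 | none | 2,823 | 0.850 | 99% |
| 0.85 | 1% | 2,847 | 0.853 | 99% |
| 0.85 | 10% | 3,074 | 0.875 | 96% |

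The 81% in the first row differs from the stated 97% because it treats 0.90 as a hazard ratio. That is a separate matter, not caused by carry-over.

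**5. As-treated follow-up.** Further assumption: 30-50% censored at day 60, then 10% per 60-day window. A true 0.90 reads 0.903-0.928 and a true 0.85 reads 0.854-0.892. For 0.85, power without carry-over is 94% (30% censored) or 89% (50% censored). With carry-over it is 83-94% or 71-87%. The drop from 99% to 89-94% comes from the assumed censoring.

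**6. Unequal repeat rates.** Assume 25% recent exacerbators in each arm, with the indicator in the model and full follow-up.
- Repeats in 10% v 20%: a true 1.00 reads 0.947, or 1.056 with the arms reversed; a true 0.90 reads 0.857 or 0.959.
- Repeats in 15% v 20%: a true 1.00 reads 0.97 or 1.03.

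The indicator does not remove this shift, because it is equally common in both arms. What differs is how often a flagged patient is re-prescribed.

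**7. The opposite case.** If treatment cuts repeats in the same ratio as new exacerbations, 0.90 reads 0.898 and 0.85 reads 0.847, so there is no dilution.

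**The case against.** **The wording may already exclude a continuing episode.** An exacerbation under treatment at entry arguably did not occur after it, and section 7.9.1 speaks of a gap between events in general terms. That may well be the intent. But the sentence sits in the paragraph on the secondary analyses, and no rule puts the intent into operation. A programmer following section 7.4.2.1 would count day +8. What stands is that this is silence: a reader might infer that the sponsor chose to count continuing episodes, and the documents do not show that.

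**The plan already handles recent exacerbation.** Matching, the propensity score and conditional adjustment limit differences between arms in who had a recent episode. If only the share of recent exacerbators differs and the indicator is in the model, a true 1.00 reads 1.00. This objection stands for confounding, not for classification of the event.

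**The size is assumed.** This stands in full. The low end is negligible. A reader might infer that the primary hazard ratio is biased towards one arm, but nothing in the documents supports a difference in repeat rates between matched arms, and the shifts to 0.947 or 1.056 need a twofold one. Nor should the 68% be read as a fall from the stated 97%; most of that distance is the separate power question.

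**A simple date rule would be flawed.** With courses on days -1, +20 and +40, a rule anchored only on pre-entry prescriptions drops day +20 and then counts day +40, although all three form one episode. Section 7.4.2.2 also speaks of a gap between courses, not between prescription dates. Both points stand and shape the fix.

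**A sensitivity analysis may already exist.** The contents list has blank entries after 7.4.2.2 and 7.9.1, and the ENCePP checklist cites page 21 for stratified analyses that are not visible. Such an analysis therefore cannot be called missing.

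**Conclusion.** The concern holds as a classification error that follows from reading the primary definition literally: the plan's own separation rule is not carried across cohort entry. That part rests on the text alone.

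Its size is unknown. Balanced carry-over unrelated to treatment leaves the null unbiased and dilutes a true effect modestly (0.90 to about 0.902-0.917 and 0.85 to about 0.853-0.875 with full follow-up, somewhat more as-treated). The 0.85 target is little affected with full follow-up. Bias in either direction is possible if repeat rates differ between arms. Randomisation does not rule that out here, but no passage indicates that it happens. This is a worthwhile, inexpensive correction, not evidence that the planned comparison is invalid.

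**What to change.** 1. State in 7.4.2.1 and 7.9.1 that the 30-day rule used for the rate outcome also defines the first primary event and applies across cohort entry. A post-entry prednisolone prescription belonging to an episode that began on or before entry is not a new event. Courses are chained until a 30-day gap occurs, and the patient stays in follow-up. Measure the gap in the same way for both outcomes. Keep counting COPD admissions as 7.4.2.1 now does, with a sensitivity analysis that applies the gap to them too.
2. Always include the 30-day pre-entry exacerbation indicator in the primary Cox model, not only if it is imbalanced, and define it to include courses dated on the entry day.
3. Unless removed text already provides it, add a sensitivity analysis excluding patients with an exacerbation in the 30 days before entry.

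**Cost.** A sentence in each of two sections, one covariate that section 7.4.3 already identifies (extended to the entry day), and the sensitivity analyses. Some genuine early moderate events go uncounted, along with any early treatment-failure signal in them. Under the assumptions above, a version of the rule without chaining loses roughly 8-27 such events per 3,000 patients; chaining may add some. Power for 0.90 falls by about 1 point.

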7.5 DATA SOURCES

The Clinical Practice Research Datalink (CPRD) will be used for this study. It includes computerized medical records of more than 12 million patients from more than 650 general practices in the United Kingdom. General practitioners, using standardized recording of medical information, record data on the patient's demographic characteristics, symptoms, history, medical diagnoses, and drug prescriptions, as well as details of referrals to specialists and hospitals. The completeness and validity of the recorded information on diagnoses, coded using READ codes, and drug exposures, coded using a coding system with a direct mapping to the NHS dictionary of medicines and devices, are checked on an ongoing basis by staff of the CPRD and have been shown in several studies [R11-2162; R16-2198]. In addition, the CPRD can be linked by unique identifier to the Hospital Episodes Statistics (HES) database which provides extensive information on all hospitalizations, coded using ICD-10 codes, including data on length of stay, ward types, as well as extensive disease and procedure coding, based on OPCS4 (Office of Population Censuses and Surveys Classification of Interventions and Procedures) codes. The linkage between the CPRD and the HES databases applies to over half of the practices contributing to the CPRD. The database has been used for the study of numerous diseases, including studies of COPD [R16-2197; P16-10095].

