7.6 BIAS

Several potential biases inherent to any observational study need to be considered. First, confounding by indication could be an issue. Matching subjects initiating LABA-TIO with subjects initiating LABA-ICS on several marker of disease, including prior COPD exacerbations, previous treatment and on the propensity score should limit this potential bias since matched subjects will have comparable probability of using either combination. In addition to matching on the propensity score, sex, prior exacerbation, prior treatment and calendar time, several variables such as general severity of COPD, comorbidity and concomitant drug use will be in the propensity score and adjusted for in the outcome model. Second, there is the possibility of information bias due to misclassification of the outcomes or exposure. CPRD contains prescriptions written by the GP rather than filled or taken by patients. This could be a source of misclassification of exposure. Another source of information bias due to the presence of hospitalizations during follow-up, particularly during the current exposure window, where GP prescriptions are not available, so that exposure is not measurable. Finally, the linkage to HES data to identify hospitalization for COPD exacerbation and for community-acquired pneumonia should reduce the potential for misclassification of outcomes.

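### Treatment choice and moderate exacerbations are both GP prescribing decisions, yet all visible adjustment is patient-level, so practice prescribing style can bias the primary HR in a direction that the documents do not settle

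*Combined protocol and SAP*

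**What the plan says.** **Outcome.** Section 7.4.2.1 defines the primary event as a hospitalization for COPD "or the prescription of an oral corticosteroid, namely prednisolone (moderate exacerbation"). The first secondary outcome (7.4.2.2) also counts courses of oral corticosteroid.

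**Exposure.** Section 7.4.1: "The exposure measures are based on the prescription of the two long-acting bronchodilators under study", and ICS likewise. Section 7.6 names the source: "CPRD contains prescriptions written by the GP rather than filled or taken by patients".

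**Matching.** Section 7.3: "We will first match subjects on sex, previous components of the study treatment (LABA only, TIO only, ICS alone, none of these"), and on the presence of an exacerbation in the prior year, within calendar-year exposure sets and then by propensity score. Section 7.4.3 repeats the list: "Sex, previous treatment and previous acute COPD exacerbation, as well as calendar year of cohort entry, are all matching factors". The score is built by "identifying all available data (e.g., diagnoses, procedures, medications) in the one-year period prior to the date of cohort entry".

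**Models.** Section 7.9.1 adds to the Cox model any patient characteristics left imbalanced and the propensity-score decile. The negative binomial model takes the same covariates.

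**Practice.** It appears only for HES linkage, end of coverage and the description of the database ("more than 12 million patients from more than 650 general practices in the United Kingdom"). Sections 7.6 and 7.11 discuss confounding by indication and misclassification, but not differences in prescribing between practices.

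**The concern.** The same prescriber decides whether a patient receives an ICS or a second bronchodilator, and whether a flare-up becomes a prednisolone prescription and so an event. If practices differ in both habits and the two habits are correlated, practice is a common cause of arm and outcome. A LABA-TIO patient can be matched to a comparator from any linked practice, so matching does not break that link. The patient's own steroid history carries some of the practice's threshold, but only through one noisy year of data.

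At stake are the primary HR and the exacerbation rate ratio. Severe exacerbation and pneumonia come from HES admissions and are less exposed.

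**Working it through.** **1. How much of the primary outcome is a prescription.** Section 7.7 expects 50% with any first exacerbation and about 15% with a severe one. Patients whose first event is severe are a subset of the 15%, so at least (50 - 15)/50 = 70% of first events are prescriptions. On the hazard scale, treating the two types as independent, the severe share is -ln(0.85)/-ln(0.50) = 0.163/0.693 = 23%, which leaves about 77% moderate. The simulations below take m = 0.8.

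**2. The plan's own figures.** The plan states no figure on practice effects. Its severe-only power reproduces: 6,000 x 0.15 = 900 events, (√900/2) x |ln 0.80| - 1.96 = 1.39, power 91.7% against a stated 92%. The 97% for HR 0.90 matches a comparison of 50% with 45% (97.3%). As a Cox HR with 3,000 events it is about 82%. That is a separate matter; HR 0.90 serves here only as a yardstick.

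**3. Size before any patient-level adjustment.** Let σu be the practice SD of the log prednisolone rate, σv the practice SD of the log-odds of LABA-ICS, and ρ their correlation. For small effects, mean log rate differs between arms by about ρσuσv, so with a true HR of 1, ln(HR) ≈ -mρσuσv. All three inputs are assumptions.

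| σu / σv | ρ | Approximate HR, unadjusted | Simulated HR, stratified on own prior moderate and severe counts |
|---|---|---|---|
| 0.2 / 0.3 | 0.3 | exp(-0.0144) = 0.986 | 0.992 |
| 0.2 / 0.3 | 0.5 | exp(-0.024) = 0.976 | 0.988 |
| 0.3 / 0.5 | 0.3 | exp(-0.036) = 0.965 | 0.983 |
| 0.3 / 0.5 | 0.5 | exp(-0.060) = 0.942 | 0.971 |
| 0.3 / 0.5 | 0.1 | exp(-0.012) = 0.988 | 0.997 |
| 0.3 / 0.5 | -0.3 | exp(+0.036) = 1.037 | 1.017 |

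The last column uses 350 practices, gamma frailty variance 0.7, 80% of hazard moderate and about 52% with an event in the year. Stratifying only on prior exacerbation yes/no gives 0.964 in the fourth row. A separate simulation that matched only on that yes/no factor gave 0.981, 0.960, 0.963 and 0.942 for the first four rows, and 1.002 at ρ = 0.

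**4. A harsher assumption.** With two practice types, the steroid-prone type having 1.5 to 2 times the prednisolone rate and supplying 40% of LABA-TIO but 60% of LABA-ICS patients, the HR after stratifying on prior count is 0.96 to 0.94. At 30% against 70% it is 0.92 to 0.88. With 60% against 40% it is 1.04 to 1.07. Adding practice type as a stratum returns 0.997 to 1.003. These values are larger because one binary type drives both habits, so ρ is in effect 1. For equal halves, a 1.5-fold rate is σu = ln(1.5)/2 = 0.20, and 40/60 is an odds ratio of 2.25, so σv = ln(2.25)/2 = 0.41.

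**5. Against the target and the noise.** ln(0.971)/ln(0.90) = 0.0294/0.1054 = 28%; ln(0.992)/ln(0.90) = 0.0080/0.1054 = 8%. With 3,000 events the SE of log HR is 2/√3000 = 0.0365 and the 95% half-width is 0.072. With no true effect, a bias to 0.97 gives z = 0.0305/0.0365 = 0.83 and a two-sided significant result about 13% of the time. At 0.99 it is about 6%, against the nominal 5%.

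**The case against.** **Direction.** A reader might infer that the omission flatters LABA-TIO. The documents do not support that. Nothing in them links readiness to prescribe prednisolone with a preference for ICS. The sign comes entirely from the assumed correlation: at zero there is no bias, and at -0.3 it runs the other way.

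**Size.** A reader might also infer a spurious HR near 0.94, more than half of the HR 0.90 effect on the log scale. That needs the strongest pair of assumed SDs with correlation 0.5, and allows only for prior exacerbation as yes/no. The plan does more. Section 7.4.3 counts prior oral corticosteroid prescriptions (adjusted for if imbalanced), respiratory antibiotics and other respiratory drugs, and 7.3 adds a high-dimensional score. This objection stands, and the count-stratified values are the fairer guide. None of the calculations models the full score. Its call on all available data could take in a practice identifier, but its examples are diagnoses, procedures and medications.

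**Hidden text.** The contents list has blank entries after 7.4.2.2 and 7.9.1, a tertiary objective is mentioned but not shown, and the checklist cites stratified analyses that are not visible. A sensitivity analysis may exist there, so the point concerns the visible main analysis only.

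**Severe-only as a control.** It is tempting to treat HES admissions as independent of GP prescribing. The documents do not show that, and earlier prednisolone could plausibly avert admissions.

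What survives is the structure: a shared prescriber, an outcome made mostly of prescriptions, and no practice-level term.

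**Conclusion.** The point holds as an uncontrolled, cheaply reducible source of possible bias in the primary HR and the exacerbation rate ratio. Its direction is unknown. Under the assumed practice SDs and correlations of 0.3 to 0.5, the null HR is about 0.97 to 0.99 after adjustment for the patient's own prior counts, and about 1.02 at correlation -0.3. That is roughly a tenth to a quarter of the HR 0.90 effect on the log scale and inside the expected confidence interval half-width. It is not negligible, because it is systematic and no larger sample removes it. Stronger practice effects would give more, and the high-dimensional score may leave less. The documents supply no figure to choose between these, which is itself a reason to measure practice prescribing. This is a recommended improvement and does not invalidate the design.

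**What to change.** In 7.4.3, add one practice-level covariate: prednisolone prescriptions per base-cohort COPD patient in the practice, leaving out the study patient and pooled over several years before entry. Include it in the propensity score and in the Cox and negative binomial models.

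Pooling is needed for stability. Section 7.7 gives about 140,000 HES-linked users over 2002 to 2012, and 7.5 implies at least about 325 linked practices: 140,000/325 ≈ 430 per practice, or about 39 per practice-year if each user is counted once, with no COPD, age or asthma restriction stated for that figure. In simulation, a rate measured on only 40 patients per practice still removed roughly half of the remaining bias.

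Matching within practice is less practical: 100,000/(325 x 11) ≈ 28 LABA-ICS users per practice-year, or about 1.8 per cell across the 2 x 4 x 2 = 16 combinations of sex, prior treatment and prior exacerbation.

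Report the severe-only HR, already powered in 7.7, beside the primary HR. Describe it as a supportive check that depends less on GP thresholds, not as a negative control. State in 7.11 that practice preference is a possible confounder of unknown direction.

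The cost is one derived variable from data already being extracted and one model term. Some confounding will remain because the practice rate is measured with error.
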